7.1.3.7 VERTICLE C/D RATIO

The vertical and horizontal C/D ratio will be assessed utilizing a 90 diopter lens during the slit lamp examination.

7.1.3.8 INDIRECT OPHTHALMIC EXAMINATIONS

The indirect ophthalmic evaluations of both the test and contralateral eyes will include assessment of:

- Evaluation of the iris
- Evaluation of the retina
- Evaluation of the vitreous
- Evaluation of the optic cup and disc
- Evaluation of the macula

Results of each of these examinations will be scored on the following scale for both the test and contralateral eyes.

- □ Normal
- ☐ Abnormal NCS Not Clinically Significant
- ☐ Abnormal CS Clinically Significant

7.1.3.9 CORNEAL ENDOTHELIAL CELL COUNT

The corneal endothelial cell count will be assessed for both the test and contralateral eye utilizing Specular Microscopy. The result will be expressed as cells/mm².

To address differences in location of the image within a given area of the cornea, three acceptable images should be taken at each visit. The density from at least one preferred image should be determined.

Non-contact specular microscopes are strongly recommended. The same model of specular microscope should be used at each site. Images should be stored on 35 mm slides, half-inch video, or in electronic format. Specular cameras that can record digitized images on disk or to e-mail are preferable for ease of data transfer.

To capture a good image:

- · make sure the subject is comfortable;
- instruct the subject to blink;
- instruct the subject not to move and to open eyes wide;
- instruct the subject to focus on the fixation light; and,
- if necessary, use the manual setting. (Note that the use of the manual setting may require additional training.)

The technician performing the image analysis should be advised of the following recommendations:

- A minimum of 100 cells (ideally 150 cells) in a contiguous area should be counted. The center method for counting cells is recommended;
- The quality of cells in an image is critical. When selecting cells to count, use the area with the fewest distortions (not in shadow, washed-out, or blurred).
- Follow the same methodology for all subjects at all visits.

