10.6 MEASURES TO MINIMIZE BIAS

10.6.1 ENROLLMENT/ RANDOMIZATION/ MASKING PROCEDURES

A study subject will be considered enrolled in the study upon signing Informed Consent. If an enrolled subject does not meet all eligibility criteria, the subject will be subsequently withdrawn from the study. Only enrolled subjects for whom an implant is attempted will be followed and reported on. Since this is a single-arm feasibility study, there will be no randomization or masking/blinding procedures.

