4.3 Additional Analyses

Signs of inflammation may indicate insufficient healing of the device within the incisional tract, allowing for micromotion of the implant and increase the risk for adverse events, including endophthalmitis. These signs of inflammation include neovascularization around the implant site, conjunctival hyperplasia (mild, moderate and marked), and partial or complete device extrusion.

Analyses will be conducted to determine whether the implant procedure characteristics described in Section 3.3 contribute to increased inflammation, and whether or not the sign of inflammation was elevated to an adverse event. Further, analyses will be performed to determine the association of inflammation with the outcomes of serious adverse events, device occlusion, and explant.

Analyses will also be conducted to determine whether different anti-inflammatory regimens for inflammation have a differential impact on subsequent adverse events, IOP, diminished flow and device useful life.

5. Subgroup Analyses

Key endpoint data (SAE, SAE or explant, IOP) may be assessed according to pre-defined subgroups. These subgroups include:

- Sex (male, female)
- Race (African American, Caucasian, other)
- Implant location (scleral, corneal)
- Allergies with ocular involvement

Other subgroups may be identified in the course of analysis and will be assessed in a *post hoc* fashion.

6. Other Information

In addition to the described data analysis, the following information will also be presented as part of the safety assessment:

- Updated endothelial cell loss (ECL) analysis
- Individual Participant Summaries for each participant
- Line listing of all adverse events
- Line listing of all protocol deviations

Subject # (Eye)	BL ECC	3 mo ECC	6 mo ECC	12 mo ECC	24 mo ECC	3 mo ECC Δ** (%Δ^^)	6 moECC Δ (%Δ)	12 mo ECC Δ (%Δ)	24 mo ECC Δ (%Δ)
##-## (OD)	####	####	####	####	####	+## (#.#)	+## (#.#)	+## (#.#)	+## (#.#)
##-## (OS)	####	####	####	####	####	+## (#.#)	+## (#.#)	+## (#.#)	+## (#.#)

^{*} ND = Not Done

 $^{^{\}wedge}$ NA = Not Applicable

^{**} A positive value indicates higher endothelial cell count relative to baseline reading, while a negative value indicates a loss in endothelial cells (ECL) since baseline

 $^{^{\}wedge \wedge}$ % Δ = (Follow-Up Visit ECC- Baseline ECC)/Baseline ECC * 100

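### Three specular images are taken per visit to offset location differences, but only one need be counted and no averaging is required, so per-eye endothelial cell changes can be noisier than they need be

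*Protocol*

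**What the plan says.** Protocol section 7.1.3.9 gives the reason for replicate images: "To address differences in location of the image within a given area of the cornea, three acceptable images should be taken at each visit". The next sentence sets the counting requirement: "The density from at least one preferred image should be determined". The term preferred is not defined, nobody is named to make the choice, and no rule turns several densities into one value.

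The same section advises the technician on three related matters:

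- Cells counted: "A minimum of 100 cells (ideally 150 cells) in a contiguous area should be counted".
- Area counted: "When selecting cells to count, use the area with the fewest distortions (not in shadow, washed-out, or blurred".
- Consistency: "Follow the same methodology for all subjects at all visits".

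Protocol section 10.6.1 says that "there will be no randomization or masking/blinding procedures". Neither document describes a masked reader or a reading centre.

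Protocol section 4.1.1 includes specular microscopy in the safety evaluation through six months. SAP section 6 lists an "Updated endothelial cell loss (ECL) analysis" among the items presented with the safety assessment. Its table has one cell count per visit, with change and percent change from baseline at 3, 6, 12 and 24 months. It does not say how that count is derived from three images.

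**The concern.** Replicate images reduce location error only if more than one of them is read. A plan that takes three and requires one count can lose the protection that it gives as its reason for taking three. The wording also sets a floor, so one visit's value may rest on a single image and another's on three.

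Elsewhere the protocol averages its replicates: three readings for central corneal thickness (section 7.1.3.4) and two for applanation tonometry (section 7.1.3.2). The cell count is the exception.

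What is at stake is the per-subject table. With ten subjects and no planned test, a reader will look at individual changes, and that is where image error weighs most. Section 2.3.1 lists corneal endothelial touch among the known potential risks, so these values will be read with some care.

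**Working it through.** The documents give no SD, CV or precision for the cell count, so there is no figure of the plan's own to reproduce. The check sizes the image-error component under stated assumptions.

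**Inputs**

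- Images taken per visit: 3. Images that must be counted: at least 1 (Protocol 7.1.3.9).
- Visits with a count: baseline and months 3, 6, 12 and 24, so 5 (Protocol Table 3; SAP section 6).
- Eyes: 2 per subject (7.1.3.9). Subjects: 10 (10.5).
- Per-image CV, s: assumed to be 4–8% of baseline.
- SD of true change between subjects, τ: assumed to be 10% of baseline for the group-mean check.

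**Step 1: image error in one eye's change.** With m independent images averaged at each visit, and s the same at both visits, SD(change) = √(2s²/m).

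- m = 1: √2 × 4 = 5.7 and √2 × 8 = 11.3 points.
- m = 3: 5.66/√3 = 3.3 and 11.31/√3 = 6.5 points.
- Relative cut: 1 − 1/√3 = 0.423, or 42%.

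This is the image-error component only. True change in the eye adds to it.

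**Step 2: limit of that gain.** If a fraction ρ of the image-error variance is shared by all images at a visit, the variance of the visit mean is s²[ρ + (1 − ρ)/3]. At ρ = 0 the cut in SD is 42%. It shrinks as ρ rises and is zero at ρ = 1. So 42% is an upper bound.

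**Step 3: group mean.** The total SD of change is √(τ² + 2s²/m). The 95% half-width at n = 10 is 2.262 × SD/√10. With τ = 10% and a wider range for s:

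| s | Half-width, one image (points) | Half-width, three images (points) |
|---|---|---|
| 2% | 7.4 | 7.2 |
| 5% | 8.8 | 7.7 |
| 10% | 12.4 | 9.2 |

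For example, at s = 5% the SDs are √(100 + 50) = 12.2 and √(100 + 16.7) = 10.8. The half-widths are then 2.262 × 12.25/√10 = 8.8 and 2.262 × 10.80/√10 = 7.7. The SD of the total falls by about 12% here, far less than 42%.

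**Step 4: cost of counting all three.** 10 subjects × 2 eyes × 5 visits × 2 further images = 200 counts at most.

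**The case against.** The strongest reply is that section 7.1.3.9 is not silent. It stresses image quality, tells the technician to use the least distorted area, and asks for the same methodology at all visits. Read in that context, preferred most plausibly means the clearest image, and a site that follows the advice should not drift between visits. This stands in part, because it reduces the freedom. However, the distortion rule governs which cells are counted rather than which of the three images is used. The consistency rule has no stated image-selection or averaging method to hold constant.

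A second reply is that the result carries limited weight. The safety endpoint is adverse event rates. SAP section 6 places cell loss under other information, SAP section 5 names serious adverse events, explant and IOP as key endpoint data, and no halting rule uses the cell count. This stands, and it sets the priority.

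A reader might infer more: that unmasked staff could pick the most favourable image and hide real loss. The expected highest of three normal values lies about 0.85 SD above the mean. Reporting the highest density at follow-up against an unselected baseline image would therefore mask 0.85 × 4 = 3.4 to 0.85 × 8 = 6.8 points. The documents do not support this as a finding. It needs someone to rank three densities and report the top one at follow-up only. If a single image is counted, the other two densities would normally be unknown. With the same selection rule at both visits, the mean bias is about zero. Nor do the documents say who chooses the image, or whether that person knows the eye and visit; absence of masking procedures does not settle it.

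**Conclusion.** The point holds as one of avoidable noise and an undefined derivation. Followed exactly, the plan allows per-eye changes that are less precise than its own required images could give, and it leaves the choice of image open.

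The size rests on the assumed CV of 4–8% and on independent error between images. Shared error shrinks the benefit, and true variation between subjects dilutes it for the group mean. Biased selection is possible under the text but is not shown.

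This is a cheap improvement to a descriptive safety listing. It does not affect the primary or secondary effectiveness endpoints.

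**What to change.** In Protocol section 7.1.3.9, replace the counting sentence with: *Density is determined on all acceptable images (target three) and the mean is recorded, at every visit and for both eyes; if fewer than three are acceptable, the mean of those available is used and the number recorded.*

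In SAP section 6, state that each visit's cell count is that mean, and show the number of images read beside it.

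The rule for fewer than three keeps a usable visit from becoming missing. Counting every acceptable image also removes the choice among them, although the choice of area within an image remains.

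The cost is up to about 200 extra counts. No new procedure or visit is needed, and because section 7.1.3.9 asks for images to be stored, past visits can be recounted.

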7.1.3.10 GONIOSCOPY

Gonioscopy evaluations will be performed on both the test and contralateral eyes. The following positions on the anterior angles will be assessed: supertemporal, superonasal, inferotemporal, and inferonasal. The results will be scored based on the Shaffer Classification:

- Grade 4: The angle between the iris and the surface of the trabecular meshwork is 45°.
- **Grade 3**: The angle between the iris and the surface of the trabecular meshwork is greater than 20° but less than 45°.
- **Grade 2**: The angle between the iris and the surface of the trabecular meshwork is 20°. Angle closure is possible.
- **Grade 1**: The angle between the iris and the surface of the trabecular meshwork is 10°. Angle closure is probable in time.
- **Slit (S)**: The angle between the iris and the surface of the trabecular meshwork is less than 10°. Angle closure is very likely.
- 0: The iris is against the trabecular meshwork. Angle closure is present.

7.1.3.11 OPTIC NERVE IMAGE ANALYSIS

The optic nerves of both the test and contralateral eyes will be imaged and analyzed by Optical Coherence Tomography (OCT). The following parameters will be measured:

- VerticalDisc Diameter
- Vertical Cup Diameter
- Superior retinal Nerve Fiber Layer (rNFL)
- Inferior retinal Nerve Fiber Layer (rNFL)
- Temporal retinal Nerve Fiber Layer (rNFL)

7.1.3.12 PERIMETRY

The visual perimetry of the contralateral non-implanted eyes will be assessed utilizing automated Humphrey Visual Field (HVF) testing. For this testing the eye should not be dilated uless it is miotic (the pupil is<3mm open). With Investigator approval, the eye may be dilated, however all remaining HVF follow-up evaluations of that eye should also be dilated. For the HFV testing the standard Swedish Interactive Thresholding Algorithm (SITA) testing algorithm should be used. +/1 mean deviations will be reported.

7.1.3.13 FLUORESCEIN STAINING

The surface and corneas of both the test and contralateral eyes will be stained with fluorescein and the surfaces examined by fluorescient light evaluation. The evaluation should be performed approximately 2.5 minutes after fluorescein instillation in the eye. The physician should use broad beam cobalt blue illumination and a yellow barrier filter hand held in front of the objective to observe corneal staining.

Based upon the evaluations, the five regions of the cornea will be scored (0-3) as shown below:

[figure not shown]

Figure 12 Corneal Fluorescein Scoring

[figure not shown]
7.1.3.14 SEIDEL'S TESTING

Topical fluorescein will be applied to the cross bar tab of each test device post-implant at each follow-up exam and observed under magnification to assess device patency (central flow) and peripheral flow. Typically, this is accomplished by wetting the sterile fluorescein strip with sterile ophthalmic topical anesthetic agent and touching the paper fluorescein applicator to the cross bar tab and vicinity of the implant site. Proper aqueous flow from the center of the cross bar tab (central flow) may be verified directly under magnification and without fluorescent lamp illumination. Fluorescent illumination with cobalt blue lamp illumination from the slit lamp or other cobalt blue light sources may enhance visualization of exiting aqueous humor.

Figure 13: Fluorescein applicator

Figure 14: Positive Seidel's Test

7.1.3.15 SCHIRMER TEAR TEST

A standard Schirmer tear test will be performed in both the test and contralateral eye to assess tear production status. The measurement interval will be 5-minutes duration.

7.1.3.16 LENS STATUS FOR PHAKIC EYES

The lens status for phakic eyes will be described for both the test and contralateral eye if applicable.

A modified LOCS III grading system utilizing a 0-5 single digit scoring system will be used to evaluate all eyes for lens changes and to evaluate those changes over time. Standardized definitions in this instrument will be used to determine "change".

7.1.3.17 TREATMENT SATISFACTION QUESTIONNAIRE

The modified Treatment Satisfaction Questionnaire (TSQ) will be given to the patient at the beginning of the follow-up visit and prior to initiation of testing procedures. The coordinator should attempt to administer the questionnaire in a consistent fashion.

This questionnaire will attempt to measure the study subject's overall satisfaction with the implanted device and procedure. Data will be summarized using simple, descriptive frequency tables.

7.1.3.18 SYMPTOM AND HEALTH PROBLEM CHART FROM CIGTS

The Symptom and Health Problem Chart from the Collaborative Initial Glaucoma Treatment Study (CIGTS)³ will be given to the patient at the beginning of the follow-up visit and prior to initiation of testing procedures. The coordinator should attempt to administer the questionnaire in a consistent fashion.

Currently permission to utilize the survey is not yet secured from the CIGTS Authors. The instrument will be administered once permission is secured prospectively only.

³ Janz, J.K; et. al. Quality of Life in Newly Diagnosed Glaucoma Patients; Ophthalmology Volume 108, Number 5, May 2001

7.2 STUDY SCHEDULE

7.2.1 SCREENING/BASELINE

Subjects will be provided with the Subject Information and Informed Consent Form which advises that data will be collected for evaluation of eligibility for inclusion in the Trial. Subjects are told that if the criteria are met and the subject consents, then the Brown Glaucoma Implant will be implanted. If the subject agrees to inclusion for data collection, the subject Informed Consent will be signed and recorded in the subject's records as part of the Screening/Baseline visit. The subject will be assigned a unique study identifier.

The Screening/Baseline evaluation may be completed after the patient has reviewed, understood, and signed the Informed Consent. The Baseline assessments may be performed at any time prior to the Implant visit. If the implanting physician determines that the subject is not a suitable candidate for the procedure, then the subject shall not be scheduled for implant, will be withdrawn from the trial, and will not be included in the analysis.

Data to be collected during the Screening/Baseline visit include:

- Informed Consent Form
- Documentation of eligibility
- Medical History (including Physical Exam)
- Medications (all medications including indication)
- Best corrected visual acuity (ETDRS)
- Applanation tonometry
- Central corneal thickness
- Diurnal IOP assessment
- Gonioscopy
- Slit lamp examination
- Indirect ophthalmic examination with dilated fundus exam
- Vertical C/D ratio assessment
- Corneal surface stain
- Optic nerve image analysis
- Corneal endothelial cell count (specular microscopy)
- · Perimetry of non implanted eye
- Lens status for phakic eyes
- Schirmer's Tear Test
- Patient body temperature

Activities to be performed:

- Answer any questions the subject may have, and confirm willingness to proceed if the baseline criteria are verified.
- Verify that the inclusion/exclusion criteria are satisfied.
- Assessment by the Investigator of the subject's suitability for BGI implant (e.g. mental fitness).

If the subject meets the inclusion criteria, the surgery for the BGI implant will be discussed with the subject and scheduled. Investigational staff will ensure the product and equipment necessary for the procedure are available, and schedule support staff.

7.2.2 IMPLANT

If Informed Consent is obtained and eligibility has been performed, the Implant visit should be scheduled. The implant should occur as soon as possible after baseline data is collected, and not more than 30 days after. Baseline data collection on the day of surgery is permitted, but must be collected prior to the surgical procedure.

Data to be collected at implant include:

- Implant location OS/OD
- Patient body temperature
- Procedure Ease
- Procedure start and end times
- Description of surgical challenges
- Seidels Test
- Device information
- Adverse Events
- Implant site photo
- Medication changes

7.2.3 FOLLOW-UP

Post-implant follow-up visits (and corresponding visit windows) will occur according to the following schedule:

- Day 1 (one day)
- Week 1 (5-9 days)
- Week 2 (11-17 days)
- Month 1 (25-35 days)
- Month 2 (50-70 days)
- Month 3 (75-105 days)
- Month 4.5 (125-150 days)
- Month 6 (168-196 days)
- Month 8 (225-255 days)
- Month 10 (285-315 days)
- Month 12 (330-390 days)
- Month 15(440-470 days)
- Month 18 (530-560 days)
- Month 21 (620-650 days)
- Month 24 (690-750 days)

Data to be collected at each visit are summarized below.

Day 1

- Applanation tonometry
- Slit lamp examination
- Seidels Test
- Body temperature
- Implant site photo
- Adverse events

Week 1

- Best corrected visual acuity (ETDRS)
- Applanation tonometry
- Slit lamp examination
- Seidel's test
- Body temperature
- Implant Site photograph
- Adverse events

Week 2

- Best corrected visual acuity (ETDRS)
- Applanation tonometry
- Slit lamp examination
- Indirect ophthalmic examination with dilated fundus exam
- Seidel's test
- Body temperature
- · Implant site photograph
- Adverse events

Month 1

- Best corrected visual acuity (ETDRS)
- Applanation tonometry
- Slit lamp examination
- · Indirect ophthalmic examination with dilated fundus exam
- Seidel's test
- Schirmer Tear Test
- Treatment Satisfaction Questionnaire (TSQ)
- Lens Status for phakic lenses
- Body temperature
- · Implant site photograph
- Adverse events

Month 2

- Best corrected visual acuity (ETDRS)
- Applanation tonometry
- Slit lamp examination
- Indirect ophthalmic examination with dilated fundus exam
- Seidel's test
- Body temperature
- Implant site photograph
- Adverse events

Early BIRD Version 9.0
Protocol 4039 27 JAN2019

Month 3

- Best corrected visual acuity (ETDRS)
- Applanation tonometry
- Slit lamp examination
- Indirect ophthalmic examination with dilated fundus exam
- Corneal endothelial cell count (specular microscopy)
- Gonioscopy
- Seidel's test
- Schirmer Tear Test
- · Lens status for phakic eyes
- Treatment Satisfaction Questionnaire (TSQ)
- Body temperature
- Implant site photograph
- Adverse events

Month 4.5

- Applanation tonometry
- Device site evaluation
- Seidel's test
- Implant site photograph
- Adverse events

Month 6

- Best corrected visual acuity (ETDRS)
- Applanation tonometry
- Central corneal thickness
- Diurnal IOP assessment
- Slit lamp examination
- Indirect ophthalmic examination with dilated fundus exam
- Vertical C/D ratio assessment
- Corneal surface stain
- · Corneal endothelial cell count (specular microscopy)
- Gonioscopy
- Optic nerve image analysis
- · Perimetry of non implanted eye
- Seidel's test
- Schirmer Tear Test
- Lens status for phakic eyes

- Treatment Satisfaction Questionnaire (TSQ)
- Implant site photograph
- Body temperature
- Adverse events

Month 8

- Applanation tonometry
- Device site evaluation
- Seidel's test
- Implant site photograph
- Adverse events

Month 10

- Applanation tonometry
- Device site evaluation
- Seidel's test
- · Implant site photograph
- Adverse events

Month 12

- Best corrected visual acuity (ETDRS)
- Applanation tonometry
- Central corneal thickness
- Diurnal IOP assessment
- Slit lamp examination
- Indirect ophthalmic examination with dilated fundus exam
- Vertical C/D ratio assessment
- Corneal surface stain
- Corneal endothelial cell count (specular microscopy)
- Gonioscopy
- Optic nerve image analysis
- · Perimetry of non implanted eye
- Seidel's test
- Schirmer Tear Test
- Lens status for phakic eyes
- Treatment Satisfaction Questionnaire (TSQ)
- Implant site photograph
- Body temperature
- Adverse events

Month 15

- · Applanation tonometry
- Device site evaluation
- Seidel's test
- Implant site photograph
- Adverse events

Month 18

- Applanation tonometry
- Device site evaluation
- Seidel's test
- Implant site photograph
- Adverse events

Month 21

- · Applanation tonometry
- Device site evaluation
- Seidel's test
- Implant site photograph
- Adverse events

Month 24

- Best corrected visual acuity (ETDRS)
- Applanation tonometry
- Central corneal thickness
- Diurnal IOP assessment
- Slit lamp examination
- Indirect ophthalmic examination with dilated fundus exam
- Vertical C/D ratio assessment
- Corneal surface stain
- Corneal endothelial cell count (specular microscopy)
- Gonioscopy
- Optic nerve image analysis
- · Perimetry of non implanted eye
- Seidel's test
- Schirmer Tear Test
- Lens status for phakic eyes
- Treatment Satisfaction Questionnaire (TSQ)
- Implant site photograph
- Body temperature
- Adverse events

